7.2.4 Composite measures of disease activity

- **Ankylosing Spondylitis Disease Activity Score (ASDAS)** (Baseline, 6-, 12- and 18-months)

The ASDAS score is a 6-item composite measure of 4 PROs and CRP or ESR:

$\text{ASDAS}_{\text{CRP}}: 0.12 \times \text{back pain} + 0.06 \times \text{duration of morning stiffness} + 0.11 \times \text{patient global} + 0.07 \times \text{peripheral pain/swelling} + 0.58 \times \text{Ln}(\text{CRP}+1)$.

$\text{ASDAS}_{\text{ESR}}: 0.08 \times \text{back pain} + 0.07 \times \text{duration of morning stiffness} + 0.11 \times \text{patient global} + 0.09 \times \text{peripheral pain/swelling} + 0.29 \times \sqrt{(\text{ESR})}$.

ASDAS_{CRP} is preferred, but the ASDAS_{ESR} can be used in case CRP data are not available. CRP in mg/L; all patient assessments on a 10 cm scale. ASDAS <2.1 is regarded as an acceptable, low disease activity level²⁵. ASDAS is also a continuous measure, which makes it appropriate to assess potential changes in disease activity, and an increase of ASDAS>0.9 is considered a clinical important worsening²⁶.

- **Bath Ankylosing Spondylitis Disease Activity Index (BASDAI)** (Baseline, 6-, 12- and 18-months)

BASDAI is a 6 item questionnaire (NRS 0-10) used to assess disease activity in ankylosing spondylitis³⁴. The score is the sum (of the first four individual questions and the mean of questions five and six) divided by five.

7.3 Safety assessments

Planned time points for all safety assessments are provided in the Schedule of Activities.

7.3.1 Physical Examinations

- General clinical examination (baseline visit)

7.3.2 **Vital signs**

- Pulse and blood pressure (baseline visit)
- Height and weight (baseline visit)

7.3.3 **Clinical Safety Laboratory Assessments** (every 3rd month and all visits)

- Haemoglobin, red blood cells, white blood cells with differential count and platelet count
- Glomerular filtration rate (GFR) and creatinin
- Alanine transaminase (ALT)

7.3.4 **Adverse Events (AEs), Serious Adverse Events (SAEs), and Other Safety Reporting**

The definitions of adverse events (AEs) and serious adverse events (SAEs) as well as the method of recording, evaluating, and assessing causality of AEs and SAEs and the procedures for completing and transmitting SAE reports are provided in Appendix 3.

7.3.5 **Time Period and Frequency for Collecting AE and SAE Information**

All AEs and SAEs will be collected from the start of intervention until the final follow-up visit at the time points specified in Schedule of Activities. Medical occurrences that begin before the start of study intervention, but after obtaining informed consent, will be recorded as Medical History/Current Medical Conditions, not as AEs. All SAEs, including updates, will be recorded and reported to the sponsor or designee immediately, as indicated in Appendix 3. Investigators are not obligated to actively seek information on AEs or SAEs after conclusion of the study participation.

7.3.6 **Method of Detecting AEs and SAEs**

Care will be taken not to introduce bias when detecting AEs and/or SAEs. Open-ended and non-leading verbal questioning of the participant is the preferred method to inquire about AE occurrences.

7.3.7 **Follow-up of AEs and SAEs**

After the initial AE/SAE report, the investigator is required to proactively follow each participant at subsequent visits/contacts. All SAEs will be followed until resolution, stabilization, the event is otherwise explained, or the participant is lost to follow-up.

7.3.8 **Regulatory Reporting Requirements for SAEs**

Prompt notification by the investigator to the sponsor of an SAE is essential so that legal obligations and ethical responsibilities are met. The sponsor has a legal responsibility to notify both the local regulatory authority and other regulatory agencies about the safety of a study intervention under clinical

investigation. The sponsor will comply with regulatory requirements relating to safety reporting to the regulatory authority, Institutional Review Board and Independent Ethics Committee.

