1.2 Schema

1.3 Schedule of Activities

Procedure	Screening		Intervention Period [remote monitoring/visits]					Extra visits and early discontinuation
			Baseline	Every month	6 th month follow-up	12 th month follow-up	18 th month Study end	
Inclusion and exclusion criteria	X							
Fulfilment ASAS criteria ¹	X							
Physical examination incl. heart and lungs	X							
Informed consent	X							
Safety laboratory tests ²		X		X	X	X	X	
CRP and ESR		X	(X ³)	X	X	X	X	
Clinical examination of disease activity, incl. enthesitis (heel), peripheral arthritis		X		X ⁴	X ⁴	X	X	
Vital signs ⁵		X						
Medical history		X						
Demography		X						
Lifestyle		X						
Patient global assessment		X	X ⁶	X	X	X	X	
Patient-reported outcomes		X	X ⁶	X	X	X	X	
Medication review		X		X	X	X	X	
Randomization		X						
Adverse event review				X	X	X	X	
Reason for discontinuation ⁷							X	

¹ The ASAS criteria include: Sacroilitis on imaging, HLA-B27 and SpA features (see 9.5.1)

² Patients using biologic medication, including the tumour necrosis factor inhibitors (TNFis), are instructed to take safety laboratory tests each 3rd month. For the “Usual care” arm, the patients will take blood tests at the 6th month visit at the hospital and take an additional blood test between these visits, which normally is prescribed and monitored by their general practitioner. For the “Remote monitoring” and “Patient-initiated care” arms, the patients are instructed to take blood tests each 3rd month, which normally is prescribed and monitored by their general practitioner. Patients, who normally take the 3-month blood tests at the hospital due to convenience, may continue this practice.

Each 6th month the patients in the two latter arms will be requested to upload a photo of the blood test results into the MyDignio app.

³ Only for the subgroup n=15 in the “Remote monitoring” arm that receive a home-based CRP instrument

⁴ At 6 and 12 months only in the “Usual care” arm

⁵ Pulse, blood pressure, body weight and height

⁶ Patients in the “Remote monitoring” arm will complete a brief questionnaire each month, and patients in the “Patient-initiated care” only each 3rd month. Longer questionnaires will be completed by all study arms each 6th month.

⁷ Only at “Early discontinuation” visit

Abbreviations: CRP: C-Reactive Protein, ESR: Erythrocyte Sedimentation Rate, HLA-B27: Human Leucocyte Antigen B27

2 Introduction

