2.3.4 Objectives and endpoints

Objectives	Endpoints
Primary	
Assess if two, new follow-up strategies are non-inferior compared to conventional follow-up with hospital visits in terms of maintaining low disease activity	Disease activity (ASDAS) at 6, 12 and 18 months
Secondary	
Compare additional measures of clinical efficacy between the treatment arms	Efficacy measures outlined in section 7.2 at each time point
Compare the safety of the two, new follow-up strategies in axSpA with the conventional follow-up strategy	Safety profile and adverse events throughout the study + doses of analgesics + prescribed antibiotics
Assess if the patients and HPs are equally adept to judge the need for consultation	Comparing the proportions that are scheduled for a visit when a serious disease activity worsening (flare) occurs
Additional	
Evaluate cost effectiveness of remote monitoring in axSpA	Health related quality of living, health care utilization and costs related to the societal perspective (e.g. work participation) as outlined in section 7.4. at each, or a combination, of time points.
Examine fluctuations in disease activity and physical activity level over time	Self-reported disease activity every month, blood tests every 6 th month, and monthly CRP for a subgroup of participants. Physical activity data from wearing an activity tracker in the two, new follow-up strategy arms
Examine if flares can be detected based on changes in monitored physical activity level	Physical activity tracker data (steps per day and minutes with moderate and high intensity activity levels) and measures of disease activity
Investigate barriers and facilitators for remote monitoring among HPs and patients	Questionnaire at baseline among HPs and patients
Investigate the HPs' and patients' perspectives and satisfaction with remote monitoring	Semi-structured interviews of 10-15 patients and their treating rheumatologist and/or nurse
Investigate HPs' and patients' experiences with video consultations, as compared to hospital visits and telephone consultations, and the impact of self-reporting on the follow-up care	Semi-structured interviews and observations of 10-15 patients and their treating rheumatologist and/or nurse

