5.1.2 Usual care arm

Patients in the “Usual care” arm will be treated according to current conventional follow-up regimen with regular hospital visits. In the ReMonit study this includes prescheduled face-to-face visits with an experienced rheumatology nurse at 6 and 12 months and with a rheumatologist at 18 months (study end), with a review of disease-related concerns, blood test results, joint examination as well as recording medication use, and adverse events.

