8.4.4 Safety Analysis

Rates and type of adverse events and serious adverse events in all three study arms will be reported.

9 Supporting Documentation and Operational Considerations

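### Adverse event review is scheduled at months 6 and 12 in every arm, but the protocol describes a contact for it only in usual care, so recording of non-serious events is likely to be unequal, chiefly in patient-initiated care

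*Protocol*

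**What the plan says.** Comparing safety is a secondary objective. Section 2.3.4 reads: "Compare the safety of the two, new follow-up strategies in axSpA with the conventional follow-up strategy". The analysis in section 8.4.4 is descriptive: "Rates and type of adverse events and serious adverse events in all three study arms will be reported".

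Section 7.3.5 has adverse events collected from the start of intervention "until the final follow-up visit at the time points specified in Schedule of Activities". In that Schedule (section 1.3) the row "Adverse event review" is marked at months 6, 12 and 18 and at extra or early-discontinuation visits, with no arm-specific footnote. The clinical examination row does carry one: "At 6 and 12 months only in the “Usual care” arm".

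Section 7.3.6 promises that "Care will be taken not to introduce bias when detecting AEs and/or SAEs" and names the means: "Open-ended and non-leading verbal questioning of the participant is the preferred method to inquire about AE occurrences".

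Section 5.1.2 gives usual care "prescheduled face-to-face visits with an experienced rheumatology nurse at 6 and 12 months" and a rheumatologist visit at month 18, with adverse events recorded. Section 5.1 mentions review of adverse events only in its description of usual care. It describes remote monitoring as review of patient-reported outcomes and blood tests, and patient-initiated care as having neither scheduled visits nor monitoring.

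**The concern.** The Schedule asks for something in all three arms that the rest of the protocol equips only one arm to do. If the month 6 and 12 reviews are not carried out in a new arm, its patients are first asked systematically at month 18, while usual-care patients are asked every six months.

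Mild or short-lived events are the ones most easily forgotten over the longer interval. A lower recorded rate in a new arm could then reflect less asking and be read as reassurance. This matters because the trial tests whether scheduled visits can be dropped, and because participants and treating staff are unblinded (section 5.2). Section 2.3.1 itself accepts that side-effects or adverse events may be missed in the two new arms. The mitigation given there is to contact patients who repeatedly fail to self-report, but none of the listed self-report items asks about adverse events.

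This is a question of data collection fixed in the protocol. No later analysis can recover events that were never elicited.

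**Working it through.** The protocol gives no adverse event rate, detection probability or safety sample size, so there is no planned figure to reproduce. The check has two parts.

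**1. What each arm is given after baseline**

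| Item (protocol section) | Usual care | Remote monitoring | Patient-initiated care |
|---|---|---|---|
| Adverse event review marked (1.3) | 6, 12, 18 | 6, 12, 18 | 6, 12, 18 |
| Scheduled visits described (5.1, 5.1.2, 7.1.6) | 6, 12, 18 | 18 | 18 |
| Adverse event review named in the arm's description (5.1 to 5.1.4) | Yes | No | No; patient is told to make contact |
| Adverse event question among listed survey and app items (7.2.1, Appendix 6) | None | None | None |
| Other routes (5.1.1, 5.1.3, Tables 1 and 2, 7.1.5, Appendix 2) | Patient contact, laboratory-triggered and unscheduled visits | The same, plus general practitioner reports, chat, weekday nurse review, BASDAI flag calls, laboratory results monitored every 6 months | Patient contact, general practitioner reports, laboratory-triggered and unscheduled visits; uploaded results used only for research after month 18 |

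The first two rows disagree for the new arms at months 6 and 12, and the third and fourth rows offer nothing that closes the gap. The medication items in section 9.5.13 ask about adherence, cortisone, NSAIDs and other analgesics, not side-effects.

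**2. Possible size, on assumptions that are not in the protocol**

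Take the case in which the month 6 and 12 reviews do not take place in a new arm. Assume the same true event rate in all arms, onset spread evenly over 18 months, and recall that decays by a constant fraction each month until the next scheduled enquiry. With k = −ln(1 − monthly loss) and w months between enquiries, the share recalled is

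cap(w) = (1 − exp(−k·w)) / (k·w), with w = 6 for usual care and w = 18 for the new arm.

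If a share s of events is reported spontaneously in every arm, the ratio of recorded events, new arm to usual care, is

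[s + (1 − s)·cap(18)] / [s + (1 − s)·cap(6)].

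| Monthly recall loss | cap(6) | cap(18) | Ratio, s = 0 | Ratio, s = 0.25 | Ratio, s = 0.5 |
|---|---|---|---|---|---|
| 2% | 0.942 | 0.838 | 0.89 | 0.92 | 0.95 |
| 5% | 0.861 | 0.653 | 0.76 | 0.83 | 0.89 |
| 10% | 0.741 | 0.448 | 0.60 | 0.73 | 0.83 |

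For example, at 5% loss and s = 0.5: (0.5 + 0.5 × 0.653) / (0.5 + 0.5 × 0.861) = 0.8265 / 0.9305 = 0.89.

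If every arm has the same enquiry at 6, 12 and 18 months, w = 6 throughout and the ratio is 1.00. The model omits chat, flag calls and laboratory review, so it describes patient-initiated care better than remote monitoring.

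**The case against.** The strongest reply is that the Schedule already requires the review in all arms. The footnote that confines the clinical examination to usual care was not placed on the adverse event row. Verbal questioning is only preferred and is not tied to visits: a telephone call is verbal, staff may call patients, and section 7.3.7 speaks of visits or contacts. Investigators record adverse events in an eCRF that is not shown. Appendix 6 is not a complete list either: the sleep item in section 7.2.1 does not appear there.

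There are other routes too. Patients in every arm are told to report adverse events, adverse laboratory results trigger a visit, general practitioners contact the hospital about safety problems, and staff may schedule visits freely. Serious events go to the sponsor immediately. The safety endpoint also covers analgesic doses and prescribed antibiotics, and analgesic use is asked of all arms every six months.

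Much of this stands, and it limits the point. A reader might infer that the plan asks usual care three times and the new arms once, and that the comparison is therefore biased in favour of both new arms. The protocol does not support that. Its Schedule nominally gives three reviews to everyone. Events can surface before month 18 without a patient's request. In remote monitoring the extra contact could even raise the number recorded. Nor can a single percentage be attached to the effect.

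The reply does not supply the missing piece: by what contact or question the month 6 and 12 reviews reach patients who have no visit then. The alternative routes also differ by arm, which is itself unequal ascertainment.

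**Conclusion.** The point holds as a gap between the Schedule and the described procedures, with a likely effect on the safety comparison. Sections 1.3, 5.1 to 5.1.4 and 7.3.5 to 7.3.6 must be reconciled.

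Unequal recording is likely for non-serious events that rely on patient recall. Under-recording is expected chiefly in patient-initiated care; for remote monitoring the net direction is uncertain. Serious events are less affected.

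The size is not computable from the protocol. The range of about 0.60 to 0.95 rests on assumed recall losses of 2 to 10% per month, an assumed spontaneous share of 0 to 50%, equal true rates, and no review at months 6 and 12 in the new arm. It shows the direction and possible scale under those assumptions and is not an estimate for this trial. If the reviews are in fact done alike in all arms, this source of imbalance disappears.

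**What to change.** Add one short adverse event question set, with the same wording and recall period, to the 6-, 12- and 18-month digital survey that all three arms already receive (section 7.2.1). State in section 7.3.6 that this is how the review in the Schedule is done in every arm, and align sections 5.1 to 5.1.4 with it.

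In section 8.4.4, base the between-arm comparison on those answers plus serious events. Report separately, by arm, events found only at usual-care visits or only at unscheduled or flag-triggered contacts, so that readers can see how much of any difference comes from the route of detection.

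The cost is a few survey items, a sentence or two in each section, and a slightly longer questionnaire. The protocol should also say who reads the answers and when, since acting on them during follow-up would add a contact in patient-initiated care. That is a clinical decision for the trial team and is not prejudged here.

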7.3.9 Pregnancy

Details of all pregnancies in female participants will be collected after the start of study intervention and until end of the study. If a pregnancy is reported, the investigator will record pregnancy information on the appropriate form and submit it to the sponsor. While pregnancy itself is not considered to be an AE or SAE, any pregnancy complication or elective termination of a pregnancy for medical reasons will be reported as an AE or SAE. Abnormal pregnancy outcomes are considered SAEs and will be reported as such. The participant will be followed to determine the outcome of the pregnancy and any post-study pregnancy-related SAE considered reasonably related to the study intervention by the investigator will be reported to the sponsor. Further participation in the study will be determined by the treating physician and principal investigator.

7.4 Health Economics

Use of health care (costs) will be captured by the following registers: The Norwegian Patient Register (hospital services), The Norwegian Prescription Register (pharmaceuticals), Norway Control and Payment of Health Reimbursement - KUHR database (primary care services), Statistics Norway's database on social benefits (FD Trygd). We will assign unit costs to each type of service by means of the diagnosis-related group (DRG) pricing system, and the price list of the Norwegian Medicines Agency. The patients will be asked about costs related to consultations, e.g., transport costs, time use, work absenteeism, need for support. We will also register the time study coordinator/nurse and rheumatologist spend on remote monitoring, telephone calls, replies to patient messages on the Dignio platform and similar. For each patient we will estimate one-year costs based on register data for utilization of health care and the unit costs. The mean quality adjusted life years (QALYs) and costs in the three arms will be used to estimate an incremental cost-effectiveness ratio (ICER) and incremental net monetary benefit (INMB).

8 Statistical Considerations

8.1 Statistical Hypotheses

Statistical hypothesis (non-inferiority test):

Null hypothesis: The point prevalence of low disease activity (ASDAS<2.1) in both “Remote monitoring” and “Patient-initiated care” is more than 15 percentage points lower than in “Usual care” arm at any follow-up time point.

Alternative hypothesis: The point prevalence of low disease activity (ASDAS<2.1) in “Remote monitoring” / “Patient-initiated care” is at most 15 percentage points lower than in “Usual care” arm at any follow-up time point.

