8.2 Sample Size Determination

Randomly assigning 80 participants to each of the three study arms will give approximately 80% power to conclude that at least one of the alternative follow-up strategies is non-inferior to conventional follow-up, using a 15% non-inferiority margin. This controls for multiple testing at the 5% level and assumes an analysis based on a logistic mixed model. We will additionally test the non-inferiority of “Patient-initiated care” to “Remote monitoring” using the same 15% margin. This test will be done only if “Patient-initiated care” is shown to be non-inferior to conventional care (a hierarchical test), and thus will not inflate the 5% false positive rate.

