8.4.1 General Considerations

- Efficacy (both primary and secondary endpoints) and safety analyses will include data from all randomised patients who started the allocated intervention by attending at least one completed questionnaire and blood test result after randomisation (FAS), and robustness analyses will be performed in the PPS.
- Demographics, baseline characteristics, efficacy and safety variables will be summarised using descriptive statistics.
- All efficacy analyses will be presented with the results from the hypothesis testing (by p-value) in addition to estimates and 95% confidence limits of the treatment effect. For the primary variables specifically, this will be the estimated mean probability with corresponding 95% confidence limits.

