8.4.2 Primary Endpoint

The primary endpoint is defined as the point prevalence of with low disease activity (defined as ASDAS <2.1) at the 6-, 12- and 18-months follow-ups.

The probability of being in low disease activity for repeated measures per individual will be used to estimate a risk difference across the three study arms. The primary variables will be analyzed using logistic regression mixed models with allocated study arm as primary explanatory variable. Other pre-specified covariates included in sensitivity analyses include age, gender, disease features. The SAP will detail these procedures, as well as alternative and further supportive evaluations, such as analyses including unbalanced baseline predictors or modifications of the regression model in case validity assumptions are not met. The primary analysis will be performed in the FAS. The primary endpoint will be evaluated by the p-value and confidence interval of the hypothesis test from the regression analysis.

In case the null hypothesis is not rejected, the new, follow-up strategies will be considered worse or inferior to usual care with hospital follow-up visits.

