8.4.3 Secondary Endpoint

Between-group comparisons will be performed for secondary efficacy endpoints.

The between-group comparisons for secondary endpoints will be tested as for the primary endpoint where applicable and additional analyses will be performed based on the following methods (but not limited to):

- Continuous secondary variables will be subject to repeated measures mixed models or appropriate non-parametric alternatives
- Binary response variables will be analyzed using logistic regression (possibly adjusting for within-subject dependencies by mixed model approaches) or other appropriate tests, e.g., chi-square/Mantel-Haenszel test

Unless otherwise specified, all statistical hypotheses will be tested as the primary endpoint, i.e., with an assessment of non-inferiority based on the p-value of the group differences.

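### Section 8.1 tests one null over both new strategies with an ambiguous visit quantifier, so rejecting it supports no conclusion about a named strategy, and 8.4.2 gives no verdict for a split result

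*Protocol*

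**What the plan says.** - **Hypotheses (8.1).** There is a single null. It begins "Null hypothesis: The point prevalence of low disease activity (ASDAS<2.1) in both", then names the two new strategies and sets a shortfall against usual care of over 15 percentage points. Its closing words are "arm at any follow-up time point". The alternative joins the two strategies with a slash, says at most 15 points lower, and ends on the same visit phrase.
- **Power and gate (8.2).** With 80 per arm the plan claims "approximately 80% power to conclude that at least one of the alternative follow-up strategies is non-inferior to conventional follow-up", with multiple testing controlled at 5%. Patient-initiated care is compared with Remote monitoring only if Patient-initiated care "is shown to be non-inferior to conventional care (a hierarchical test").
- **Analysis (8.4.1, 8.4.2).** The modelled probability of low disease activity "will be used to estimate a risk difference across the three study arms". For the primary variables, 8.4.1 says "this will be the estimated mean probability with corresponding 95% confidence limits". Neither sentence names a visit, all visits or an average over visits.
- **Verdict (8.4.2).** Only non-rejection is covered: "the new, follow-up strategies will be considered worse or inferior to usual care".
- **Carry-over (8.4.3).** Unless otherwise specified, other hypotheses are tested like the primary endpoint, "with an assessment of non-inferiority based on the p-value of the group differences".

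**The concern.** A non-inferiority trial with two experimental arms has to be able to say which arm met the margin. The null as written joins the two arms, so its rejection is a statement about the pair. The gate in 8.2 needs a statement about Patient-initiated care alone, and 8.1 provides none. If one strategy meets the margin and the other does not, 8.4.2 has no conclusion to offer. If the null is not rejected, 8.4.2 calls both strategies worse or inferior, although non-rejection shows only that non-inferiority was not demonstrated.

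The visit wording adds a second uncertainty. The endpoint is measured at 6, 12 and 18 months, and 8.1 does not settle whether a strategy must meet the margin at all three visits or at just one. The same data can then give opposite primary conclusions depending on how the sentence is read.

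**Working it through.** **1. Strategies.** Let A = Remote monitoring is beyond the margin and B = Patient-initiated care is beyond the margin. The written null is A and B. Rejecting it gives not-A or not-B: at least one is non-inferior. That agrees with the power target in 8.2. The gate needs not-B, which does not follow.

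Example: Remote monitoring truly at 88% and Patient-initiated care just beyond the margin at 72.9%. At a single visit the joint null is rejected in 75.1% (one-sided 0.0125) to 83.2% (0.025) of trials, while Patient-initiated care passes its own test in 1.2–2.5%.

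Even the agreement with the power target depends on scope. If the visit phrase governs *both*, different strategies may pass at different visits (84.2% against 82.0% at 0.025, correlation 0.5).

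**2. Visits.** The same word *any* stands in null and alternative. Two pairings are complementary:

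| Null | Alternative | Rule |
|---|---|---|
| beyond margin at some visit | within margin at every visit | all visits |
| beyond margin at every visit | within margin at some visit | one visit suffices |

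A visit average is a third possible rule. It is not a reading of 8.1; it arises only because the risk difference in 8.4.2 and the mean probability in 8.4.1 are not tied to a visit.

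**3. Inputs.** From the protocol: 80 per arm and a 15-point margin. Assumed: 88% in usual care (given in 3.2 for two-year follow-up and not linked to 8.2); exchangeable visit correlation ρ = 0.3, 0.5, 0.7; one-sided alpha per comparison 0.025, or 0.0125 after halving for two comparisons; no dropout; no adjustment across visits.

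**4. Formulas.** With 88% in each arm, SE per visit = √(2·0.88·0.12/80) = 0.0514. Single-visit power per strategy at 0.025 = Φ(0.15/0.0514 − 1.960) = Φ(0.96) = 83.1%. For a visit average, the SE is multiplied by √((1+2ρ)/3); at ρ = 0.5 it is 0.0420, and power = Φ(3.575 − 1.960) = 94.7%. The other results come from 400,000 normal draws of the visit estimates with a shared control arm.

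**5. Results (%, for ρ = 0.3 / 0.5 / 0.7).** Both strategies truly equal to usual care, except in the last row.

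| | 0.025 | 0.0125 |
|---|---|---|
| All visits, per strategy | 62.5 / 66.2 / 70.3 | 49.0 / 53.9 / 59.1 |
| All visits, at least one strategy | 79.3 / 82.1 / 84.9 | 66.9 / 71.2 / 75.8 |
| All visits, exactly one strategy passes | 33.8 / 31.7 / 29.2 | 35.8 / 34.7 / 33.0 |
| Average, per strategy | 97.9 / 94.7 / 90.3 | 96.1 / 90.9 / 84.6 |
| Average, at least one strategy | 99.6 / 98.7 / 96.9 | 99.1 / 97.1 / 94.0 |
| A strategy passes average, fails all visits | 35.4 / 28.4 / 20.0 | 47.1 / 37.0 / 25.5 |
| One visit suffices: false claim for at least one, both at 72.9% | 12.2 / 11.0 / 9.5 | 6.5 / 5.9 / 5.2 |

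The reverse of the sixth row (passes all visits, fails average) is about 0%. A correlated-binary simulation with estimated standard errors gives 34.4 / 27.8 / 19.2 and 45.6 / 35.6 / 24.4 for the sixth row.

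**6. The plan's 80%.** It cannot be reproduced uniquely, because 8.2 gives no control rate, visit correlation or per-comparison alpha. At 88% and 0.025 the all-visits rule is closest (79–85% for at least one strategy). But a single-visit test gives 81.2% at a rate of 80% and 0.025, and the average rule gives 81.1% at a rate of 80%, 0.0125 and ρ = 0.7.

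**The case against.** **Separate tests are plainly intended.** The slash in the alternative, the gate and the multiplicity statement all point that way. This is right about intent, and it limits the severity. It does not repair 8.1, where the null says otherwise.

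**The gate is already stated correctly.** A reader might infer that rejecting the joint null would open the third test and inflate its error. The documents do not support that: 8.2 makes the condition specific to Patient-initiated care, so in a split result where that strategy fails, no third test is run. What is missing is the null whose rejection meets the condition.

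**The all-visits rule is the only coherent reading.** It is not. The one-visit-suffices pairing is equally complementary, so logic alone does not select the rule.

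**The plan adopts a visit average.** A reader might infer this from 8.4.1. The phrase there may mean no more than the model-estimated probability per arm, and the difference in 8.4.2 is across arms, not across visits. The average remains an open possibility only because no contrast is named.

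**The SAP will settle it.** 8.4 and 8.4.2 defer technical detail, and the absence of a contrast alone would be a weak point. The hypotheses, however, are fixed in the protocol in words that allow opposite rules, so a SAP would have to choose between them or depart from the text.

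**Conclusion.** The point holds as a defect in the stated hypotheses and verdict rule. The joint null cannot support a conclusion about a named strategy, and 8.4.2 is silent on a split result. On the all-visits rule, exactly one strategy would pass in about 29–36% of trials even if both truly equal usual care.

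The visit phrase allows one visit to suffice. Under that reading a false claim occurs in about 10–12% of trials at one-sided 0.025 and 5–6.5% at 0.0125, with both strategies just beyond the margin. If the contrast turned out to be a visit average, a strategy would pass it and fail the all-visits rule in about 20–35% or 25–47% of trials.

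These sizes rest on the assumed 88% rate, the visit correlation, the alpha per comparison and no dropout; the logical points do not. The stated 80% power leans towards the all-visits rule but neither proves it nor is shown to be wrong. Because a sensible intention can be inferred, this should be fixed, but it does not show that the gate or the design is invalid.

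**What to change.** **8.1.** Write one null and one alternative for each strategy against usual care. Replace the visit phrase with one explicit quantifier that excludes the one-visit-suffices reading. For example, H0: more than 15 points lower at one or more of the three visits; H1: at most 15 points lower at all three. If a visit average is what is meant, state both hypotheses on that average.

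**8.4.2.** Name the matching risk-difference contrast. Give the verdict per strategy as non-inferiority shown or not shown, in place of worse or inferior. Report the risk difference with confidence limits at each visit, whichever rule is chosen.

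**8.2.** Tie the existing gate to rejection of the Patient-initiated care null. State the power under the chosen rule with its control rate, visit correlation and one-sided alpha per comparison.

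**Cost.** Wording in three sections, with no new data or visits. The quoted power may look less favourable: under the assumptions above, an all-visits rule has 49–70% power per strategy. An average rule has more power but can mask a shortfall at one visit, which is why the visit-level results should stand beside it.
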